10.3 ANALYSIS PLAN

The data collected in this study will be presented in listings and tables. No inferential statistical analyses are planned. Presentations will be appropriate to the data analyzed. Summary statistics may include the mean, N, standard deviation, median, minimum, maximum, the 25th and 75th percentile values for continuous variables, and frequencies and

percentages for categorical variables. Confidence intervals may be included for informal purposes.

Medical history and prior/concomitant medications will be coded using the World Health Organization Drug Dictionary (WHODrug), and AEs will be coded using the Medical Dictionary for Regulatory Affairs (MedDRA). Coding dictionary versions will be specified in the SAP.

All statistical analyses will be performed by the Sponsor's biostatistics department personnel (or appropriate designees) using SAS®, Version 9.3 or higher, or other validated software.

10.3.1 Efficacy Endpoint(s)

There are no efficacy measures since this is an observational study.

10.3.2 PGI-S Questions Assessment

The primary objective is to characterize the psychometric properties and performance of 3 PGI-S questions (Appendix 15.1) in PAH subjects during pre-ISWT, at the end of activity, and through recovery.

The focus of the analyses will be to describe PGI-S measurement sensitivity of the subjects' self-reported symptoms of PAH at the end of the activity and during recovery from activity. The Sponsor will tabulate symptom scores and compute changes from baseline (pre-activity) scores for each question. Data may be displayed graphically and will be summarized overall and by cohort and sequence/period (as appropriate).

Additionally, for Cohort A, the sensitivity to a known inhaled treprostinil drug effect will be assessed tabulating, across time, the PGI-S measurements with inhaled treprostinil to PGI-S measurements without inhaled treprostinil. Test-retest assessments for PGI-S measurements will be conducted for Cohort B.

Correlations between the 3 PGI-S questions and with Borg dyspnea scores, oxygen saturation, and HR will be assessed. Data for HR recovery at 1 minute after the ISWT will be examined in an exploratory fashion overall and as related to PGI-S measurements.

The onset and recovery profile for activity-induced symptoms will also be characterized.

10.3.3 Safety Analyses

Safety will be evaluated on AEs, vital signs, and oxygenation. All AEs as recorded by the Investigators will be assigned a MedDRA Preferred Term and System Organ Class by the Sponsor for reporting purposes. The summary of AEs will include the number and percentage of subjects, as well as the number of events reported for each Preferred Term. No inferential analyses are planned for the AEs.

Data collected at pre-ISWT will serve as baseline values for the evaluation of data collected during ISWT and recovery. Summary statistics will be calculated for measured values and changes from baseline values. No inferential analyses are planned on these safety endpoints.

10.4 INTERIM ANALYSIS

There is no planned interim analysis for the study. However, given the open-label nature of the study, results may be tabulated by the Sponsor during the course of the study.

10.5 OTHER ANALYSES

Other analyses may be conducted based on available study data. Details for any other planned statistical analyses will be specified in the SAP.

10.6 DATA LISTINGS AND SUMMARIES

All scientifically relevant data gathered in this study will be presented in summary tables and listings in the clinical study report.

11 PACKAGING AND FORMULATION

11.1 CONTENTS OF STUDY DRUG

Not applicable. This is an observational study and no investigational drug will be administered.

11.2 LABELING

Not applicable. This is an observational study and no investigational drug will be administered.

11.3 STORAGE AND HANDLING OF CLINICAL STUDY MATERIAL

Not applicable. This is an observational study and no investigational drug will be administered.

11.4 SUPPLY AND RETURN OF CLINICAL STUDY MATERIAL

Not applicable. This is an observational study and no investigational drug will be administered.

11.5 DRUG ACCOUNTABILITY

Not applicable. This is an observational study and no investigational drug will be administered.

12 REGULATORY AND ETHICAL OBLIGATION

12.1 US FDA OR APPLICABLE REGULATORY REQUIREMENTS

The study will be conducted in accordance with International Council for Harmonisation (ICH), Good Clinical Practices (GCP) guidelines, and all applicable national regulations. The Sponsor will obtain the required approval from the regulatory authority to conduct the study. During the conduct of the study, an annual safety report will be compiled by the Sponsor for submission to those regulatory authorities and IRBs/IECs that require it. Any additional national reporting requirements specified by the applicable regulations, regulatory authorities, or IRB/IEC will also be fulfilled during the conduct of the study.

12.2 INFORMED CONSENT REQUIREMENTS

Before a subject is enrolled in the study, the Investigator or his/her designees must explain the purpose and nature of the study, including potential benefits and risks and all study procedures to the subject. The subject must sign and date an IRB/IEC-approved ICF prior to the conduct of any study-related activities. A copy of the signed consent form will be given to the subject, and the original will be retained in the study site's records.

12.3 INDEPENDENT ETHICS COMMITTEE/INSTITUTIONAL REVIEW BOARD

Prior to study initiation at each site, the Investigator will obtain approval for the study from an appropriate IRB/IEC and provide the Sponsor or designee with a copy of the approval letter. The IRB/IEC must also review and approve the study site's ICF and any other written

information provided to the subject prior to enrollment, as well as any advertising materials used for subject recruitment. Copies of the site-specific ICF and advertising materials must be forwarded to the Sponsor or designee for review before submission to the IRB/IEC and prior to the site starting the study.

If, during the study, it is necessary to amend either the protocol or the ICF, the Investigator is responsible for obtaining IRB/IEC approval of these amended documents prior to implementation. Copies of the IRB/IEC correspondence and approval letters must be sent to the Sponsor or designee.

During the conduct of the study, an annual progress report will be compiled by the Sponsor for submission to those IRBs/IECs that require it.

A written summary of the study will be provided by the Investigator to the IRB/EC following study completion or termination according to the IRB/IEC standard procedures. Additional updates will also be provided in accordance with the IRB/IEC's standard procedures.

12.4 PRESTUDY DOCUMENTATION REQUIREMENTS

Before the commencement of the clinical study, the following documents will be provided to the site: protocol, ICF, budget agreement, and eCRF.

The site will be required to provide the following documents to United Therapeutics Corporation's (UTC's) designee (Lung Biotechnology PBC) prior to study start: signature page of the protocol, Form FDA 1572, Financial Disclosure Form, IRB/IEC Composition and Roster, IRB/IEC protocol and informed consent approval letters, and Curriculum Vitae of study staff listed on the 1572.

12.5 SUBJECT CONFIDENTIALITY

Every effort will be made to keep medical information confidential. UTC, Lung Biotechnology PBC, the FDA or other regulatory bodies, and the IRB/IEC governing this study may inspect the medical records of any subject involved in this study. The Investigator may release the subject's medical records to employees or agents of the Sponsor, the IRB/IEC, or the FDA or appropriate local regulatory agencies for purposes of checking the

accuracy of the data. A number will be assigned to all subjects, and any report published will not identify the subject's name.

13 ADMINISTRATIVE AND LEGAL OBLIGATIONS

13.1 PROTOCOL AMENDMENTS AND STUDY TERMINATION

Protocol amendments that could potentially affect the safety of participating subjects or that alter the scope of the investigation, the scientific quality of the study, the experimental design, duration of therapy, assessment variables, the number of subjects treated, or subject selection criteria may be made only after consultation between UTC, its designee (Lung Biotechnology PBC), and the Investigator.

All protocol amendments must be submitted to and approved by the appropriate regulatory authorities and IRB/IEC prior to implementation.

A report documenting study termination must also be submitted to and acknowledged by the appropriate IRB/IEC for each study site.

At the end of the study, where applicable, a final report will be provided to the local regulatory agencies.

13.2 STUDY DOCUMENTATION AND STORAGE

In accordance with federal/national regulations, ICH, and GCP guidelines, the Investigator must retain study records for at least 2 years after the last approval of a marketing application in an ICH region and until there are no pending or contemplated marketing applications in an ICH region, or at least 2 years have elapsed since the formal discontinuation of clinical development of the investigational product. The Investigator must notify UTC or its designee, Lung Biotechnology PBC, before any disposal or change in location of study records.

13.3 STUDY MONITORING AND DATA COLLECTION

In accordance with federal/national regulations, ICH, and GCP guidelines, monitors for UTC or its designee, Lung Biotechnology PBC, will periodically contact the site and conduct on-site visits. During these visits, the monitor will, at a minimum, confirm ethical treatment

of subjects, assess study progress, review data collected, conduct source document verification, verify drug accountability periodically, and identify any issues requiring resolution.

The Investigator agrees to allow the monitor direct access to all relevant documents and to allocate his/her time and his/her staff to the monitor to discuss any findings or any relevant issues.

13.4 QUALITY ASSURANCE

The Sponsor is responsible for ensuring that the study is conducted and data are generated, documented, and reported in compliance with the protocol, GCP guidelines, and applicable regulatory requirements.

The Sponsor or a contracted representative of the Sponsor may conduct a quality assurance audit of this study. If such an audit occurs, the Investigator agrees to allow the auditor direct access to all relevant study documents and source data and to allocate time to discuss findings and any relevant issues. In addition, this study is subject to an audit by the relevant Regulatory Authorities. If such a regulatory inspection occurs, the Investigator agrees to allow the inspector direct access to all relevant study documents and source data.

15 APPENDICES

15.1 PATIENT GLOBAL IMPRESSION OF SEVERITY (PGI-S) QUESTIONS

[figure not shown]
[REDACTED]

[REDACTED]

[figure not shown]
[REDACTED]

[REDACTED]

[REDACTED]

[REDACTED]

15.2 INCREMENTAL SHUTTLE WALK TEST

Standardization

Standardization of the ISWT is very important for obtaining meaningful outcomes. It is advisable to time the performance as an additional measure, to confirm manual recording of the number of shuttles completed.

Please note that:

- If a repeat test is performed on the same day, at least a 1-hour rest should be allowed between tests.
- Only standardized instructions from the provided media should be used.
- No encouragement should be given throughout the ISWT.
- A comfortable ambient temperature and humidity should be maintained for all tests.
- The walking track must be the same for all tests for a patient:
 - Cones are placed 9 meters apart.
 - The distance walked around the cones is 10 meters.

The total number of shuttles completed by a subject during the Screening ISWT will be the maximum targeted for that subject during the remaining ISWTs in the study.

Before the ISWT

- Instruct the patient to dress comfortably and to wear appropriate footwear.

During the ISWT

Follow the instructions:

The objective of the ISWT is to walk as long as possible, there and back, along the 10-meter course (identified for the patient by 2 cones with an insert of 0.5 meters from either end), keeping to the speed indicated by the beeps on the audio recording.

Instructions for the subject: You will hear these beeps at regular intervals. You should walk at a steady pace, aiming to turn around the cone at 1 end of the course when you hear the first beep, and at the other end when you hear the next. At first, your walking speed will be very slow, but you will need to speed up at the end of each minute. Your aim should be to follow

the set rhythm for as long as you can. Each single beep signals the end of a shuttle and each triple beep signals an increase in walking speed. You should stop walking only when you become too breathless to maintain the required speed or can no longer keep up with the set pace.

The test is maximal and progressive. In other words, it is easier at the start and harder at the end. The walking speed for the first minute is very slow. You have 20 seconds to complete each 10-meter shuttle, so don't go too fast. The test will start in 15 seconds, so get ready at the start now. Level 1 starts with a triple beep after the 4-second countdown.

Ending the ISWT

The ISWT ends if any 1 of the following occur:

- The patient is **more than** 0.5 meters away from the cone when the beep sounds (allow 1 lap to catch up to the pace of the audio recording).
- The patient reports that they are too breathless to continue.

At the End of the ISWT

- Seat the patient or, if the patient prefers, allow the patient to stand.
- Record 1 of the following reasons for terminating the test (the patient can be asked, "What do you think stopped you from keeping up with the beeps?"):
 - Shortness of breath
 - Physical fatigue
 - Chest pain
 - Other

The patient should remain in a clinic area for at least 15 minutes following an uncomplicated test.

Modified from <https://pulmonaryrehab.com.au/patient-assessment/assessing-exercise-capacity/incremental-shuttle-walking-test/>

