6.12 SUPPORTIVE ANALYSES

6.12.1 *Borg Dyspnea Score*

Summary statistics will be computed to characterize average change and variability overall and by cohort and sequence/period (as appropriate). The pre-ISWT (average of -15 and 0 minutes), post-ISWT at each time point, and pre-post difference for Borg Dyspnea score will be provided. Summary statistics will include the mean, N, standard deviation, median, mode, minimum, maximum, the 25th and 75th percentile values, and 95% confidence intervals for the mean and difference values.

6.12.2 *Pulse Oximetry and Heart Rate*

Summary statistics will be computed to characterize average change and variability overall and by cohort and sequence/period (as appropriate). The pre-ISWT (average of -15 and 0 minutes), post-ISWT at each time point, and pre-post difference for oxygenation and HR will be provided. Summary statistics will include the mean, N, standard deviation, median, mode, minimum, maximum, the 25th and 75th percentile values, and 95% confidence intervals for the mean and difference values.

6.12.3 *ISWT*

Tabulations will be provided by cohort and sequence/period (as appropriate) for the total number of shuttles completed, total distance walked (meters), use of oxygen during ISWT (Yes, No), reason for ISWT ending (Shortness of breath, Physical fatigue, Chest pain, Other), and time since most recent dose of PAH medication (Start time of ISWT - Time of most recent dose of PAH medication).

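### Protocol Appendix 15.2 caps later walks at the Screening shuttle count, but its script, end list and termination reasons make no provision for reaching that count

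*Protocol*

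**What the plan says.** The cap is stated in Protocol Appendix 15.2 under Standardization: the number of shuttles completed at Screening "will be the maximum targeted for that subject during the remaining ISWTs in the study". Protocol 3.1, Protocol 3.3.4.1 and SAP 3.1 say the same.

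The conduct parts of Appendix 15.2 read differently:

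- **Aim:** "The objective of the ISWT is to walk as long as possible".
- **Script read to the subject:** "You should stop walking only when you become too breathless to maintain the required speed", or when the pace is lost. It adds: "The test is maximal and progressive". Sites may use only the standardized instructions on the supplied media, and the appendix gives no separate script for Day 1.
- **End list:** two events. Either the subject is too far from the cone at the beep (with one lap allowed to catch up), or "The patient reports that they are too breathless to continue".
- **Termination reasons:** shortness of breath, physical fatigue, chest pain or other. Staff may ask the patient what prevented them from staying with the beeps.

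SAP 6.12.3 carries the same four categories into the tables as "reason for ISWT ending (Shortness of breath, Physical fatigue, Chest pain, Other", together with shuttles completed and distance, by cohort and sequence/period.

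**The concern.** The cap and the conduct rules define two different tests. Under the cap, a Day 1 walk has an upper limit on work, and a subject may finish it with symptoms below their own limit. Under the script and end list, the subject walks to a symptom or pace limit, however many shuttles that takes.

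The PGI-S score at completion means something different in each case. When two walks both stop at the same cap, a difference in symptoms is a difference at equal work. When both run to the subject's limit, end symptoms tend to be similar, and any benefit may show as extra shuttles instead.

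SAP 6.11.2 compares the completion change score between Periods 1 and 2 in Cohort B. SAP 6.11.3 compares it between inferred peak and trough in Cohort A. If sites read the appendix differently, or if cap stops cannot be identified, these comparisons mix the two kinds of score and a reader cannot sort them out.

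**Working it through.** The point turns on text, and the plan gives no figure to reproduce. The check sets the cap against each operative element, then asks what the planned records would show.

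**Step 1. Does any operative element provide for reaching the Screening count?**

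| Element | Entries | Entries that cover the cap |
|---|---|---|
| End list (Protocol 15.2) | 2: behind the pace; too breathless | 0 of 2 |
| Stop conditions in the script (Protocol 15.2) | 2: too breathless for the speed; cannot keep pace | 0 of 2 |
| Termination reasons (Protocol 15.2, SAP 6.12.3) | 4: three symptoms and *Other* | 0 of 4 by name; *Other* can hold it |

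**Step 2. Apply the text to a subject who is still on pace at the Screening count on Day 1.** No end rule is met and the script says to go on. The Standardization statement says that this count is the maximum. The two instructions cannot both be followed.

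**Step 3. What would the recorded data show?** Compare the Day 1 count with the Screening count:

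- *Below:* the cap was not reached, and the walk ended for another reason.
- *Above:* the cap was not applied. The counts reveal this afterwards, but the completion score already comes from a longer walk.
- *Equal:* ambiguous. The subject was stopped at the cap, or reached a symptom or pace limit on that same shuttle.

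In the equal case, the recorded reason is the only planned item that could decide. *Other* is consistent with a cap stop but also holds every unlisted cause. A symptom code is consistent with a true symptom limit, but also with a cap stop where the optional question led the patient to name a symptom. That question presumes the patient failed to keep pace, which is untrue of a cap stop. SAP 6.12.3 summarizes counts by group and plans no within-subject comparison with Screening.

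**Step 4. Extent of exposure.** About 40 subjects × 2 Day 1 walks = 80 walks. Protocol 5.2 enrolls equal numbers in the two cohorts, so each paired comparison rests on about 40 / 2 = 20 subjects. The share of walks that would reach the Screening count is not given and cannot be derived from the documents.

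**The case against.** The strongest reply has five parts.

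1. **The cap is in the appendix.** It stands under Standardization, ahead of the conduct steps, so staff have the instruction. The line about when to stop is addressed to the subject and does not forbid staff to end the walk. This stands: a reader might infer that the appendix ignores the cap, and it does not. What remains is that the script and end list do not carry it out, which invites uneven practice between sites.
2. ***Other* is available.** A reader might infer that every capped walk is recorded as though a symptom ended it. The documents do not support that: *Other* is a valid non-symptom code in both documents, and the leading question is optional. The supported claim is narrower: a cap stop has no category of its own.
3. **Count and reason together say a good deal.** An overrun would show, and an equal count coded *Other* points toward a cap stop. This stands in part. The inference is indirect, and it fails where *Other* holds another cause or the reason is miscoded.
4. **A maximum does not equalize work.** Subjects may stop short of it in either period, so work could differ even with the cap strictly applied. This stands. The documents do not say that the cap is meant to hold Day 1 work constant, nor whether the targeted maximum is a hard stop.
5. **The stakes are modest.** SAP 6.10 plans no hypothesis testing, and the ISWT table is supportive. But SAP 6.11.2 and 6.11.3 fall under the primary PGI-S analysis and report 95% confidence intervals, so what the completion score represents still matters.

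The eCRF and the supplied media are not among the documents. The eCRF may already have a free-text field or an item for reaching the target.

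**Conclusion.** The concern holds as a conflict between stated rules. Appendix 15.2 sets a maximum that its own aim, script and end list do not carry out, and none of the four termination reasons names it. The consequence takes one of two forms for any given walk, never both: the walk runs past the Screening count, or it is stopped there and coded without a category of its own. In either case, cap-limited and symptom-limited completion scores cannot be reliably separated in the SAP 6.11.2 and 6.11.3 comparisons.

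About 80 Day 1 walks are exposed. The number affected, and any shift in a PGI-S estimate, cannot be stated from the documents. The conclusion assumes that at least some subjects are still on pace at their Screening count on Day 1, and that the eCRF follows the four categories in the SAP. The point should be fixed, but it does not undermine the study as a whole.

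**What to change.** - **Reconcile Appendix 15.2** so that the cap statement, aim, script and end list agree on whether reaching the Screening count ends a Day 1 walk. Carry the same reading into Protocol 3.1, Protocol 3.3.4.1 and SAP 3.1. Which reading applies is for the sponsor to settle.
- **Add a termination reason**, such as *Screening shuttle number reached*, in Appendix 15.2, SAP 6.12.3 and, if not already there, the eCRF. Word the optional question so that it also fits a subject who did not fall behind.
- **Tabulate the completion PGI-S change** with and without that reason, by period in Cohort B and by peak and trough in Cohort A.

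The cost is protocol and SAP wording, at most one extra eCRF category, and one table split. No new assessment or extra subject is needed.

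### The shuttle-walk script gives a subject with chest pain, dizziness or faintness who can still keep pace no instruction to stop, and the listed ending conditions do not add one

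*Protocol*

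**What the plan says.** The incremental shuttle walk test (ISWT) is the study's means of bringing on symptoms. It is done once at Screening and twice on Day 1 (Protocol Sections 3.1 and 3.3.4.1). Appendix 15.2 governs all three walks.

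- **Script for the subject.** The subject is to follow "the set rhythm for as long as you can" and to "stop walking only when you become too breathless to maintain the required speed or can no longer keep up with the set pace". The script then describes the test as maximal.
- **Ending conditions.** The lead-in is "The ISWT ends if any 1 of the following occur", and two conditions follow. One is being over half a metre short of the cone at the beep, with one lap allowed to recover the pace. The other is "The patient reports that they are too breathless to continue".
- **After the walk.** Staff are told "Record 1 of the following reasons for terminating the test", and the options are shortness of breath, physical fatigue, chest pain and other. SAP Section 6.12.3 tabulates them. The appendix adds "The patient should remain in a clinic area for at least 15 minutes following an uncomplicated test".
- **Delivery.** "Only standardized instructions from the provided media should be used". Staff give no encouragement during the walk.
- **Cap.** The Screening shuttle count is the ceiling for both Day 1 walks. No ceiling is stated for Screening.

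**The concern.** Section 1.1 lists chest pain, dizziness and syncope among the ways PAH presents, and reports that patients rank dizziness among the symptoms that affect daily life most. The study imposes a maximal walk on these patients, including those in WHO Functional Class III, in order to provoke symptoms. Yet the word *only* in the script limits the subject's stated grounds for stopping to breathlessness and loss of pace. A subject who feels faint or has chest pain, but is still reaching each cone on time, hears nothing that tells them to stop. What is at stake is subject safety during a study procedure. No estimate is at stake.

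**Working it through.** The check is a comparison of texts. The plan has no figure to reproduce.

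**Step 1. Script against ending list.** Each gives two grounds, and they match: breathlessness and pace. Neither names chest pain, dizziness, faintness, a request to stop, or staff judgement.

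**Step 2. Search for a walk-level stop elsewhere.**

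| Provision | Where | Does it say when to end a walk? |
|---|---|---|
| Chest pain and Other as recorded reasons | Appendix 15.2; SAP 6.12.3 | No. It shows that such endings are foreseen, but it is recorded after the walk has ended |
| Continuous oximetry | Protocol 3.3.2.3, 7.1.2 | No. There is no SpO2 or heart-rate threshold |
| Adverse events assessed during the walk | Protocol 3.2, 7.1.2 | No. It requires assessment and gives no stop rule |
| Investigator judgement of urgent need | Protocol 3.3.4.1 | No. It concerns starting supplemental oxygen |
| Right to withdraw at any time | Protocol 8.1 | No. It applies to the study as a whole |
| Stopping the study or a site | Protocol 8.2, 8.3 | No. It applies at study or site level |
| Exclusions 3, 6 and 9; Class I to III limit | Protocol 4.1, 4.2 | No. They act at entry |
| No encouragement | Appendix 15.2 | No. It removes pressure from staff to go on |

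Across the visible text the count is two stop conditions (pace and breathlessness), and none for chest pain, dizziness or faintness, for a subject's request, for staff judgement, or for a physiological limit.

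**Step 3. Is the list exclusive?** No. Its lead-in states what is enough to end the test and does not say that nothing else may. It also omits the Day 1 stop at the Screening shuttle count, which plainly ends a walk. The reference to an uncomplicated test implies that complicated ones are expected.

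**Step 4. Number of walks under the script.** Walks per enrolled subject: 1 Screening + 2 Day 1 = 3. For 40 subjects: 40 × 3 = 120 walks, of which 40 × 1 = 40 are at Screening and 40 × 2 = 80 are on Day 1. Screen failures and rescreens add to the Screening number. These are walks done under the wording; they are not walks harmed by it.

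**Step 5. What an earlier stop could cost.** Inclusion criterion 5 requires 3 shuttles. For the first minute the script says "You have 20 seconds to complete each 10-meter shuttle", so the minimum is reached after 3 × 20 s = 60 s. Only a stop within the first minute would affect eligibility.

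**The case against.** The strongest reply is that the pace condition already covers these symptoms. It is not tied to a cause. The suggested prompt after the walk asks what kept the subject from matching the beeps, and chest pain is one of the offered answers. A subject who halts for any reason therefore meets an ending condition. This stands, and it limits the point to what the subject is told while still able to keep pace.

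A second reply is that the spoken instructions come from media that are not in the documents, and that the consent discussion must cover risks and procedures (Section 12.2). This also stands. The media may already contain the missing sentence, so the first action is to check them.

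A third is that an amendment to a standardized test in a small single-day study is not free, and that a mid-study change would give subjects different instructions. That is fair, but the added wording matters only to subjects with warning symptoms.

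Three stronger readings are tempting and unsupported:

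- *Staff may not stop a walk, or subjects must go on.* Nothing forbids staff to intervene, the list is not exclusive, and halting satisfies the pace condition.
- *The wording makes subjects walk through symptoms.* That it discourages stopping is an inference from one word. The documents hold no data on its effect.
- *The problem lies mainly in the uncapped Screening walk.* The same script governs all three walks, and the Day 1 cap equals the subject's own Screening maximum, so it is not a submaximal limit.

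**Conclusion.** The point holds as a gap in the subject's instruction and in the list of ending conditions, and it applies equally to all three walks. In the visible text, a subject with chest pain, dizziness or faintness who can still keep pace is given no instruction to stop. No walk-level rule covers those symptoms, a request to stop, or a judgement by staff that going on is unsafe.

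This is a cheap patient-safety improvement. No event rate is claimed, and no planned analysis changes. The conclusion assumes that the provided media say no more than Appendix 15.2; if they do, the remaining task is to bring the appendix into line with them.

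**What to change.** 1. In the script, delete *only* and tell subjects to stop also for chest pain, dizziness or feeling faint.
2. Under the ending conditions, add that the test ends if the subject reports any of these, asks to stop, or site staff or the Investigator judge it unsafe to continue.
3. Check the provided media and align them if they lack this wording.

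The existing reason categories can record such endings, so no new data field or table is needed.

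The cost is a short amendment to Appendix 15.2 with regulatory and IRB/IEC approval (Section 13.1) at up to 20 centers (Section 3.4), plus reissued media if they need changing. A few walks may end earlier. At Screening, an earlier stop lowers that subject's Day 1 target, and a stop before 3 shuttles makes the subject ineligible.
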